2.5.5.2.3. Unsolicited AEs by PT

The following summary tables of unsolicited TEAEs will be provided by PT sorting by frequency on the mRNA-1010 group:

- All unsolicited TEAEs
- SMQ

2.5.5.2.4. Unsolicited AEs by Severity

The following summary tables of unsolicited TEAEs will be provided by severity using frequency counts and percentages:

- All unsolicited TEAEs
- All unsolicited treatment-related TEAEs

2.5.5.2.5. Independent Cardiac Event Adjudication Committee

An independent CEAC of medically qualified personnel, including cardiologists, will review suspected cases of myocarditis and pericarditis to determine if they meet CDC criteria of "probable" or "confirmed" events, and to assess severity (see more details in the protocol Section 5.1.6.2) and provide the assessment to the Sponsor. The CEAC members will be blinded to study treatment. Details regarding the CEAC composition, responsibilities, procedures, and frequency of data review can be found in the CEAC charter.

A summary table will be provided based on the data adjudicated by the CEAC, as the primary analysis of cardiac events.

2.5.5.2.6. Subgroup Analysis of Unsolicited AEs

Analysis of unsolicited TEAEs will be conducted for subgroups defined in Table 5. Overall summary of the unsolicited TEAEs up to 28 days will be provided for each subgroup. Summary tables for TEAE, treatment-related TEAEs, and SAEs by SOC and PT may also be provided for each subgroup up to 28 days after the vaccine.

2.5.5.3. Death

Total number of deaths due to any cause and time of death from injection (numeric and by time point window) may be summarized in a table. A listing will be provided.

2.5.5.4.1. Pregnancy

Pregnancy testing is scheduled to occur at the Screening Visit and Day 1. Individuals who have a positive pregnancy test at the Screening Visit and Day 1 must not be enrolled. Additional pregnancy testing may also be performed at any time during the study if required by local regulatory requirements, or at the discretion of the investigator. Pregnancy test results will be listed by participant.

2.5.5.4.2. Vital Signs

Vital signs including systolic and diastolic blood pressures, pulse rate, respiratory rate, and body temperature will be measured at the time points indicated in the SoA (Section 7.1). Abnormal vital sign measurements will be graded per toxicity grading criteria provided in Section 7.7. Vital signs may be collected at other clinic/in-person visits in conjunction with a symptom-directed physical examination. The preferred route of temperature assessment is oral.

Observed value and change from pre-injection (baseline) to post-injection in vital signs will be summarized by vaccination group. Abnormal vital sign measurements will be graded per toxicity grading criteria provided in Section 7.7. A toxicity grade shift table of the vital signs from pre-injection to post-injection will be provided. Additionally, the values that are outside the reference ranges will be flagged in a data listing. Participant with any abnormal vital sign measurement where toxicity grade (Grade 3 or higher) will be listed separately.

2.5.6. Exploratory Analysis

2.5.6.1. Frequency of RT-PCR-Confirmed Protocol-Defined ILI

Number and percentage of participants with RT-PCR confirmed protocol-defined influenza infection (See Section 2.5.3.5) within the period of 14 days post-injection up to EoS will be summarized for the Safety Set. A 2-sided 95% CI using the Clopper-Pearson method will be provided for the percentage of participants with the RT-PCR confirmed influenza infection.

2.5.6.2. Biomarker Analysis

Biomarkers may be evaluated for safety and/or vaccine efficacy using left over samples that include serum collections and NP swab. Transcriptomics or genomics may be evaluated as an optional assessment from participants that consent to providing the samples. Participants who do not wish to have their samples analyzed for transcriptomics may still participate in the study.

The biomarker analysis will not be covered in this plan and will be developed in a separate plan as needed.

2.5.6.3. COVID-19 Impact

For Part A, Part B, and Part C, a listing will be provided for the impact of COVID-19 on the execution of the study.

2.5.7. Planned Analyses

2.5.7.1. Primary Analysis

The primary analysis of immunogenicity and safety will be performed after all participants have completed the Day 29 Visit. All data relevant to the primary study analysis through the Day 29 Visit will be cleaned for the primary analysis (i.e., data that are as clean as possible) and a report may be generated.

The analysis will be performed by a separate team of unblinded programmers and statisticians. More details can be found in the study data blinding plan.

2.5.7.2. Final Analysis

Final analysis of all immunogenicity and safety data will be performed once all participants complete the Day 181 (Month 6)/EoS Visit.
3. Part B

3.1. Study Objectives

3.1.1. Primary Objectives

The primary objective is to evaluate:

- The humoral immunogenicity (for noninferiority) of mRNA-1010 relative to that of a licensed SD seasonal influenza vaccine (Fluarix Quadrivalent) against 4 vaccine-matched influenza virus A and B strains at Day 29 in adults 18 to <65 years old.
- The reactogenicity and safety of mRNA-1010.

3.1.2. Secondary Objectives

The secondary objective is to evaluate:

- The immunological response of mRNA-1010 (for superiority) relative to that of a licensed SD seasonal influenza vaccine (Fluarix Quadrivalent) against vaccine-matched influenza virus A and B strains at Day 29.
- To further evaluate the humoral immunogenicity of each study arm against vaccine-matched influenza virus A and B strains at Day 29.

3.1.3. Exploratory Objectives (May be Performed)

The following exploratory objectives may be performed:

- To evaluate humoral immunogenicity of mRNA-1010 relative to that of a licensed SD seasonal influenza vaccine (Fluarix Quadrivalent) vaccine-matched influenza virus A and B strains at Day 181/EoS in a subset of participants.
- To evaluate the humoral immunogenicity of mRNA-1010 relative to that of a licensed SD seasonal influenza vaccine (Fluarix Quadrivalent) against vaccine-matched or vaccine-mismatched A and B strains.

3.2. Study Endpoints

3.2.1. Primary Endpoints

The primary objectives will be evaluated by the following endpoints:

- Immunogenicity endpoints:
 - GMT at Day 29 as measured by HAI.
 - Proportion of participants reaching seroconversion at Day 29 as measured by HAI.
 GMT and rate of seroconversion will be evaluated for each individual A and B strain (A/H1N1, A/H3N2, B/Victoria, and B/Yamagata). Therefore, there will be eight co-primary immunogenicity endpoints in the study.
- Reactogenicity and safety endpoints:
 - Frequency and grade of solicited local and systemic reactogenicity ARs during a 7-day follow-up period post-injection.
 - Frequency and severity of any unsolicited AEs during the 28-day follow-up period postinjection.
 - Frequency of any SAEs, MAAEs, and AESIs from Day 1 to Day 181/EoS.

3.2.2. Secondary Endpoints

- GMT at Day 29 as measured by HAI.
- Proportion of participants reaching seroconversion at Day 29 as measured by HAI.
- The proportion of participants with HAI titer \geq 1:40 at Day 29.
- GMFR comparing Day 29 to Day 1 (Baseline) as measured by HAI.

3.2.3. Exploratory Endpoints

The exploratory objectives may be evaluated by the following endpoints:

- GMT at Day 181 as measured by HAI.
- Proportion of participants reaching seroconversion at Day 181 as measured by HAI.
- GMT and GMFR of nAbs by assays such as MN assays or alternative methods against vaccine-matched/mismatched strains on Day 29 compared with Day 1 (Baseline).

• GMT and GMFR of anti-HA antibodies as measured by HAI against vaccine-mismatched strains on Day 29 compared with Day 1 (Baseline).

3.3. Study Design

3.3.1. Overall Study Design

Part B is a Phase 3, randomized, stratified, observer-blind, active-controlled study to evaluate the safety and reactogenicity of mRNA-1010 seasonal influenza vaccine in adults 18 to <65 years old.

The mRNA-1010 to be tested contains 4 mRNAs in an equivalent mRNA mass ratio that encode membrane-bound HA of the 4 different influenza strains recommended by WHO for 2023-2024 NH cell- or recombinant-based vaccines. The licensed SD seasonal influenza vaccine, Fluarix Quadrivalent contains 4 HAs of the 4 different influenza strains recommended by the WHO for 2023-2024 NH egg-based vaccines.

Approximately 3000 participants will be randomly assigned to treatment in this study in a 1:1: ratio to 1 of 2 treatment groups to receive either a single dose of mRNA 1010 or a single dose of a licensed SD seasonal influenza vaccine (Fluarix Quadrivalent, Table 7).

Table 7 Treatment Groups and Dose Levels (Part B)

Treatment Group	Study Intervention Received	mRNA/Antigen HA (each) (μg)	Total Dose (μg)	Number of Participants
3	mRNA-1010	12.5 (of mRNA)	50 (of mRNA)	1500
4	Active Comparator (Fluarix Quadrivalent)	15 (of protein)	60 (of protein)	1500

Abbreviations: HA=hemagglutinin; mRNA=messenger ribonucleic acid

Clinic/in-person visits will consist of a Screening Visit (up to 28 days before the Day 1 visit and may be performed over multiple visits if within the 28-day screening window), a dosing visit on Day 1 (Baseline; may be on the same day as the Screening Visit), a visit on Day 29 (Month 1), and a subsequent visit on Day 181 (Month 6)/EoS (in a subset of ~1000 participants) with up to 7 months of study participation for each participant. There will also be contacts by electronic means or telephone calls on Day 8, Day 91 (Month 3), and Day 181 (non-subset participants) (Month 6).

3.3.2. Statistical Hypotheses

The primary objective in Part B is to evaluate the noninferiority of the immunogenicity response to mRNA-1010 versus the licensed SD Fluarix Quadrivalent, as measured by GMT and seroconversion rate at Day 29 using HAI assay, for all 4 vaccine-matched influenza virus A and B strains:

• For each of the 4 vaccine-matched strains, the noninferiority hypothesis in terms of the GMT is:

Null Hypothesis: H₀¹: GMR \leq 0.667 (inferior) vs. Alternative Hypothesis: H₀¹: GMR >0.667 (noninferior) Using a noninferiority margin of 1.5, where the GMR is the ratio of the GM HAI titer in the mRNA 1010 group compared with the GM HAI titer in the Fluarix Quadrivalent group.

• For each of the 4 vaccine-matched strains, the noninferiority hypothesis in seroconversion rate is:

Null Hypothesis: H_0^2 : SCR differences $\leq -10\%$ (inferior) vs.

Alternative Hypothesis: H_0^2 : SCR differences > -10% (noninferior)

Using a noninferiority margin of 10%, where the SCR difference is the difference in the SCR between the mRNA 1010 group compared with the Fluarix Quadrivalent group.

The noninferiority hypotheses in the GMT and SCR will be evaluated for all 4 strains and Part B is considered a study success if all the 8 coprimary immunogenicity endpoints meet the noninferiority criteria. Therefore, each of the coprimary immunogenicity endpoints will be tested at 1-sided alpha of 0.025 level:

- For each strain, the noninferiority in GMT will be demonstrated by the lower bound of the 95% CI of the GMR ruling out 0.667, ie. the lower bound of the 95% CI >0.667
- For each strain, the noninferiority in SCR will be demonstrated by the lower bound of the 95% CI of the SCR difference ruling out -10%, ie. the lower bound of the 95% CI >-10%

ModernaTX, Inc. mRNA-1010-P303

Upon successful demonstration of noninferiority for Part B, ie. the noninferiority success criteria have been met for all 8 coprimary immunogenicity endpoints, the following superiority hypotheses will be tested:

• For each of the 4 vaccine-matched strains, the superiority hypothesis in terms of the GMT is:

Null Hypothesis: H_0^3 : GMR = 1 vs. Alternative Hypothesis: H_0^3 : GMR >1 (superior)

• For each of the 4 vaccine-matched strains, the superiority hypothesis in seroconversion rate is:

Null Hypothesis: H_0^4 : SCR differences = 0 vs.

Alternative Hypothesis: H_0^4 : SCR differences >0 (superior)

The multiplicity adjustment procedures for the superiority tests of the 8 immunogenicity endpoints are specified in Section 3.5.4 (also see Figure 1).

3.3.3. Sample Size and Power

Assuming approximately 15% of 3000 randomized participants will be excluded from the PP Immunogenicity Set, with approximately 2550 participants in the PP Immunogenicity Set (1:1 ratio; approximately 1275 participants in each treatment group):

- The study has at least 99% power to meet the noninferiority success criteria in GMT for all 4 strains at a 1-sided alpha of 0.025 level with a noninferiority margin of 1.5. An underlying GMR (mRNA-1010 vs. the licensed Fluarix SD Quadrivalent vaccine) of 0.90 is assumed for each of the 4 strains and the standard deviation of the natural log-transformed levels is assumed to be 1.5.
- The study has at least 98% power to meet the noninferiority success criteria in SCR for all 4 strains, at a 1-sided alpha of 0.025 level with a noninferiority margin of 10%. The SCRs of 58% for influenza A strains and SCRs of 48% for influenza B strains, respectively, are assumed in the mRNA 1010 group, whereas the SCRs in the licensed SD Fluarix Quadrivalent group are assumed to be 59% and 49% for the influenza A and B strains, respectively.

ModernaTX, Inc. mRNA-1010-P303

The overall power for achieving the primary noninferiority objective in Part B would be approximately 98%. Furthermore, the sample size provides 1) an approximately 79.5% power for a superiority test of GMT for an individual strain with an underlying GMR of 1.2 (mRNA-1010 vs. Fluarix SD Quadrivalent); 2) an approximately 63% power for a superiority test of SCR for an A strain (assuming an SCR of 64% for mRNA-1010 vs. 59% for Fluarix SD Quadrivalent), and an approximately 61% power for a superiority test of SCR for a B strain (assuming an SCR of 54% for mRNA-1010 vs. 49% for Fluarix SD Quadrivalent) at 2-sided alpha of 0.025 (with alpha split for multiplicity adjustment).

3.3.4. Randomization

Randomization will be performed using an IRT. Approximately 3000 participants will be randomly assigned to treatment in this study in a 1:1 ratio to 1 of 2 treatment groups to receive either a single dose of mRNA-1010 or a single dose of a licensed SD seasonal influenza vaccine (Fluarix Quadrivalent, Table 7). Randomization will be stratified by previous flu season (since September 2022) vaccination status (Received; Received from mRNA-1010-P302, Not received).

3.3.5. Blinding and Unblinding

See Section 2.3.5 for details.

3.4. Analysis Sets

See Section 2.4 for details.

3.5. Statistical Analysis

3.5.1. General Considerations

SoA is presented in Section 7.1.2. Additional details are presented in Section 2.5.1.

For the Day 29 primary analysis, the analysis will include all participants' safety data collected up to Day 29 post-vaccination.

Subgroups:

Subgroup Variable*	Categories
Age Group	≥ 18 to <50 years old
	\geq 50 to <65 years old
Previous Flu Season Vaccination	Received
Status	Received from mRNA-1010-P302
	Not Received
Race	White
	Black or African American
	Asian
	American Indian or Alaska Native
	Native Hawaiian or Other Pacific Islander
	Other (combining Not Reported and Unknown)
Sex	Male
	Female
BMI (only for immunogenicity	$<30 \text{ kg/m}^2$
analyses)	$\geq 30 \text{ kg/m}^2$

Table 8 Definition for Subgroups (Part B)

*Subgroup derivations will be based on the information from eCRF.

If the number of participants in a subgroup is less than 10% of sample size in the analysis set, it may be combined with other subgroups for the subgroup analyses.

3.5.2. Background Characteristics

3.5.2.1. Participant Disposition

See Section 2.5.2.1 for details.

3.5.2.2. Demographics and Baseline Characteristics

Descriptive statistics for age, weight, height, and BMI are described in Section 2.5.2.1.

The number and percentage of participants will be provided for the following categorical variables:

- Age group (18 to <50 years old, ≥ 50 to <65 years old)
- Sex (Male, Female)
- Race (White, Black or African American, Asian, American Indian or Alaska Native, Native Hawaiian or Other Pacific Islander, Other, Unknown, Not reported)

- Ethnicity (Hispanic or Latino, Not Hispanic or Latino, Not Reported, Unknown)
- Previous Flu Season Vaccination Status (Received, Received from mRNA-1010-P302, Not Received)

The summaries will be provided separately for all analysis sets (except for Solicited Safety Set) defined in Section 3.4.

3.5.2.3. Medical History

See Section 2.5.2.3 for details.

3.5.2.4. Prior and Concomitant Medications and Vaccinations

See Section 2.5.2.4 for details.

3.5.2.5. Protocol Deviations

See Section 2.5.2.5 for details.

3.5.2.6. Study Exposures

See Section 2.5.2.6 for details.

3.5.3. Immunogenicity Analysis

Immunogenicity analyses for Part B will be conducted using the PP Immunogenicity Set.

3.5.3.1. Analysis of Primary Endpoints

- GMT as measured by HAI against 4 vaccine-matched influenza virus A and B strains at Day 29 (noninferiority testing)
- Proportion of participants reaching seroconversion at Day 29 as measured by HAI (noninferiority testing)

See Section 2.5.3.1 for details.

3.5.3.2. Supplementary Analysis

The primary analyses will be repeated using the Immunogenicity Set as a supplementary analysis.

3.5.3.3. Subgroup Analysis

To assess the consistency of immunogenicity response of mRNA-1010 across subgroups, subgroup analysis of the co-primary endpoints may be conducted by subgroups defined by age group, previous flu vaccine status, race, sex, and BMI category (see Table 8), based on the PP Immunogenicity Set. For each subgroup category, the co-primary immunogenicity endpoints will be analyzed using the same statistical methods as for primary analysis. Additional details are documented in Section 2.5.3.1.

If the number of participants in a subgroup is less than 10% of sample size in the analysis set, it may be combined with other subgroups for the subgroup analyses.

3.5.3.4. Analysis of Secondary Endpoints

• GMT as measured by HAI against vaccine-matched influenza virus A strains at Day 29 (superiority testing)

Upon successful demonstration of noninferiority for Part B, superiority of mRNA-1010 relative to a licensed SD seasonal influenza vaccine (Fluarix Quadrivalent) against vaccine-matched influenza A strains (A/H1N1 and A/H3N2) at Day 29 will be tested at a two-sided $\alpha = 0.025$ level. The same ANCOVA model for primary immunogenicity analysis will be applied. The superiority of GMT in participants who received mRNA-1010 compared to GMT in participants who received Fluarix Quadrivalent will be demonstrated by the lower bound of the 97.5% CI of the GMR ruling out 1 (lower bound > 1).

• Proportion of participants reaching seroconversion at Day 29 as measured by HAI against vaccine-matched influenza virus A strains (superiority testing)

If superiority has been demonstrated based on GMT for vaccine-matched influenza A strains, the SCR of the vaccine-matched influenza A strains at Day 29 between the vaccination groups will be compared. The Miettinen-Nurminen's method will be used to calculate the 97.5% CI for the difference in SCRs. The superiority of SCR will be considered demonstrated if the lower bound of the 97.5% CI of SCR difference is > 0.

ModernaTX, Inc. mRNA-1010-P303

• GMT as measured by HAI against vaccine-matched influenza virus B strains at Day 29 (superiority testing)

Upon successful demonstration of superiority (either one or both hypotheses) for vaccinematched influenza A strains, superiority of mRNA-1010 relative to a licensed SD seasonal influenza vaccine (Fluarix Quadrivalent) against vaccine-matched influenza B strains (B/Victoria and B/Yamagata) at Day 29 will be tested:

- If both GMT and SCR hypotheses for vaccine-matched influenza A strains are successful, testing for vaccine-matched influenza B strains will be performed at a two-sided $\alpha = 0.025$ level.
- \circ If only one of GMT and SCR hypotheses for vaccine-matched influenza A strains is successful, testing for vaccine-matched influenza B strains will be performed at a two-sided α =0.0125 level.

The same ANCOVA model for primary analysis will be applied. The superiority of GMT in participants who received mRNA-1010 compared to GMT in participants who received a licensed SD seasonal influenza vaccine (Fluarix Quadrivalent) for vaccine-matched influenza B strains will be demonstrated by the lower bound of the 97.5% or 98.8% CI of the GMR ruling out 1 (lower bound > 1).

• Proportion of participants reaching seroconversion at Day 29 as measured by HAI against vaccine-matched influenza virus B strains (superiority testing)

If superiority has been demonstrated based on GMT for vaccine-matched influenza B strains, the SCR of the vaccine-matched influenza B strains at Day 29 between the vaccination groups will be compared at the same α level. The Miettinen-Nurminen's method will be used to calculate the 97.5% or 98.8% CI for the difference in SCRs. The superiority of SCR will be considered demonstrated if the lower bound of the 97.5% or 98.8% CI of SCR difference is > 0.

• The proportion of participants with HAI titer \geq 1:40 at Day 29

The number and percentage of participants with a HAI titer ≥1:40 post-vaccination will be provided with 2-sided 95% CI using the Clopper-Pearson method.

• GMFR comparing Day 29 to Day 1 (Baseline) as measure by HAI

Descriptive statistics (n, median, min, max) will be provided for the GMFR of HAI titers with corresponding 95% CI at Day 29 over Day 1 (Baseline). The 95% CIs will be calculated based on the t-distribution of the log-transformed values then back transformed to the original scale for presentation. In addition, the GMFR with corresponding 95% CI will be plotted at Day 29.

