2.5.3. Immunogenicity Analysis

For immunogenicity analysis, antibody titers reported as below the LLOQ will be replaced by 0.5 x LLOQ. Values that are greater than the ULOQ will be converted to the ULOQ.

The primary analysis population for immunogenicity will be the PP Immunogenicity Set, unless otherwise specified. The primary objective of this study is to use the immunogenicity response to infer efficacy in participants receiving mRNA-1010, see Section 2.3.2 for statistical hypotheses.

Immune responses, as measured by GMT and seroconversion rate in the mRNA-1010 group based on Day 29 HAI titers, will be compared to that in participants receiving the active comparator for all 4 strains.

Rate of seroconversion is defined as the proportion of participants with either a pre-vaccination HAI titer <1:10 and a post-vaccination titer \geq 1:40 or a pre-vaccination HAI titer \geq 1:10 and a minimum 4-fold rise in post-vaccination HAI antibody titer.

The primary immunogenicity estimands are presented in detail in Table 17. The Day 29 primary analysis of immunogenicity will be performed after all participants have completed the Day 29 visit.

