2.5.3.1. Analysis of Primary Endpoints

 GMT as measured by HAI against 4 vaccine-matched influenza virus A and B strains at Day 29

The GMT will be calculated using the following formula:

$$GMT = 2^{\left\{\frac{\sum_{i=1}^{n} \log_2(t_i)}{n}\right\}}$$

where, for n participants, t_i is the immunogenicity titer measurement for participant i.

An ANCOVA model will be carried out. The model will include the log-transformed HAI titers at Day 29 as the dependent variable, treatment group as the fixed variable, log-transformed baseline HAI titers as a fixed covariate, adjusting for the stratification factors. The GLSM and its corresponding 95% CI results in log-transformed scale estimated from the model will be back-transformed to obtain these estimates in the original scale, as an estimate of the GMT.

The GMR for mRNA-1010 vs. active comparator, estimated by the ratio of GLSM and the corresponding 2-sided 95% CI will be provided to assess the treatment difference and calculated by back-transforming of the difference estimated from the ANCOVA model. The corresponding 2-sided 95% CI of GMR will be provided to assess the difference in immune response between the mRNA-1010 group compared to the active comparator group at Day 29. For each strain, the noninferiority of GMT will be considered demonstrated if the lower bound of the 95% CI of the GMR is >0.667 based on a noninferiority margin of 1.5.

Descriptive statistics (n, median, min, max) will also be provided for the GMT of HAI titers with corresponding 95% CI at each timepoint. The 95% CIs will be calculated based on the t-distribution of the log-transformed values then back transformed to the original scale for presentation. In addition, the GMT with corresponding 95% CI will be plotted at each time point respectively.

• Proportion of participants reaching seroconversion at Day 29 as measured by HAI

The number and percentage of participants with seroconversion at Day 29 will be provided with 2-sided 95% CI using the Clopper-Pearson method. To compare the seroconversion rates between the treatment groups, the Miettinen-Nurminen's method will be used to calculate the 95% CI for the difference in seroconversion rates at Day 29. For each strain, the noninferiority of seroconversion rate will be considered demonstrated if the lower bound of the 95% CI of the seroconversion rate difference is > -10% based on a noninferiority margin of 10%.

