4.3.3. Sample Size and Power

Assuming approximately 15% of 3000 randomized participants will be excluded from the PP Immunogenicity Set, with approximately 2550 participants in the PP Immunogenicity Set (1:1 ratio; approximately 1275 participants in each treatment group):

- The study has at least 99% power to meet the noninferiority success criteria in GMT for all 4 strains at a 1-sided alpha of 0.025 level with a noninferiority margin of 1.5. An underlying GMR (mRNA-1010 vs. the licensed Fluzone HD Quadrivalent vaccine) of 0.90 is assumed for each of the 4 strains and the standard deviation of the natural log-transformed levels is assumed to be 1.5.
- The study has at least 93% power to meet the noninferiority success criteria in SCR for all 4 strains, at a 1-sided alpha of 0.025 level with a noninferiority margin of 10%. The SCRs of 58% for influenza A strains and SCRs of 48% for influenza B strains, respectively, are assumed in the mRNA 1010 group, whereas the SCRs in the licensed Fluzone HD Quadrivalent group are assumed to be 60% and 50% for the influenza A and B strains, respectively.

The overall power for achieving the primary noninferiority objective in Part C would be approximately 93%. Furthermore, the sample size provides 1) an approximately 79.5% power for a superiority test of GMT for an individual strain with an underlying GMR (mRNA-1010 vs. Fluzone HD Quadrivalent) of 1.2; 2) an approximately 43% power for a superiority test of SCR for an A strain (assuming an SCR of 64% for mRNA-1010 vs. 60% for Fluzone HD Quadrivalent), and an approximately 41% power for a superiority test of SCR for a B strain (assuming an SCR of 54% for mRNA-1010 vs 50% for Fluzone HD Quadrivalent) at 2-sided alpha of 0.025 (with alpha split for multiplicity adjustment).

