Target Population	Adults aged at least 18 years inclusive and less than 65 years who receive the assigned IP administration, complied with immunogenicity blood sampling to have a baseline and Day 29 antibody assessment after the IP administration, and have no major protocol deviations impacting the immune response.	Adults aged at least 18 years inclusive and less than 65 years who receive any IP administration and complied with immunogenicity blood sampling to have a baseline and Day 29 antibody assessment.
Endpoint	Seroconversion rate difference of antibody measured by HAI assay on Day 29.	As per Estimand 2a.
Treatment Conditions	mRNA-1010 vs. active comparator (Fluarix Quadrivalent)	As per Estimand 2a.
Population-Level Summary	Immune response to influenza defined as seroconversion rate difference of antibody using Miettinen-Nurminen's method.	As per Estimand 2a.
Intercurrent Event Strategy		

IcEv1 (early discontinuation or unrelated death)	Principal stratum	Principal stratum	
IcEv2 (alternative influenza vaccine)	Principal stratum	Treatment policy	
IcEv3 (COVID-19 vaccine)	Principal stratum	Treatment policy	
IcEv4 (prohibited medications)	Principal stratum	Treatment policy	
IcEv5 (early infection)	Principal stratum	Treatment policy	
IcEv6 (wrong vaccination)	Principal stratum	Treatment policy	

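### The SCR superiority tests in Parts B and C are valid but unadjusted; using baseline titre as a covariate would recover some power, about 2 to 5 points under mid-range assumptions

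*SAP*

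**What the plan says.** In SAP 3.5.3.4 (Part B) each GMT superiority test is followed by an SCR superiority test.

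- **SCR, A strains:** "The Miettinen-Nurminen's method will be used to calculate the 97.5% CI for the difference in SCRs".
- **SCR, B strains:** "The Miettinen-Nurminen's method will be used to calculate the 97.5% or 98.8% CI for the difference in SCRs". The level depends on the A-strain results.
- **GMT:** "The same ANCOVA model for primary immunogenicity analysis will be applied". SAP 2.5.3.1 gives that model "log-transformed baseline HAI titers as a fixed covariate, adjusting for the stratification factors".

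For the coprimary SCR comparison, the estimand table in SAP 7.8 gives the same unadjusted summary: "Immune response to influenza defined as seroconversion rate difference of antibody using Miettinen-Nurminen's method". The supplementary analysis in SAP 3.5.3.2 changes only the analysis set, and no adjusted SCR analysis is planned.

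SAP 2.5.3 builds baseline titre into the endpoint. Seroconversion means reaching 1:40 from a baseline below 1:10, or otherwise a "minimum 4-fold rise in post-vaccination HAI antibody titer". SAP 2.4 requires a baseline HAI result for the Immunogenicity Set, and hence for the PP Immunogenicity Set.

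Part C takes the same methods from SAP 4.5.3.4, which lists only the A-strain GMT test but refers to 3.5.3.4, and from SAP 4.5.4, which applies the Figure 1 order.

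Stated power is "an approximately 63% power for a superiority test of SCR for an A strain" in Part B and "an approximately 43% power for a superiority test of SCR for an A strain" in Part C. The B-strain figures are 61% and 41%.

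**The concern.** Baseline titre is complete, measured before dosing, and likely to predict who seroconverts. It is a covariate in one half of each GMT/SCR pair and not in the other, and the SAP gives no reason. In a randomised comparison, adjusting for a prognostic baseline value narrows the interval for the same marginal difference.

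The SCR superiority tests have the lowest stated power in the plan. As SAP 3.5.3.4 is worded, a failed A-strain SCR test after a successful A-strain GMT test also halves the two-sided alpha for the B strains, from 0.025 to 0.0125. Precision given up at the A-strain SCR step therefore carries forward.

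**Working it through.** **Inputs from the documents** (SAP 3.3.3 and 4.3.3): n = 3000 × 0.85 / 2 = 1275 per arm; two-sided alpha 0.025, so z = 2.2414; Day 29 SD on the natural-log scale 1.5. The SCR pairs appear in the table below.

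**Step 1. Reproduce the stated power with no covariate.**

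Power = Φ{[δ − z·√(2p̄(1−p̄)/n)] / √([p₁(1−p₁) + p₂(1−p₂)]/n)}

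For 64% vs 59%, p̄ = 0.615. The pooled SE is √(0.47355/1275) = 0.01927 and the unpooled SE is √(0.4723/1275) = 0.01925. Then (0.05 − 2.2414 × 0.01927)/0.01925 = 0.35, and Φ gives 63.8%. The other three pairs give 61.2%, 43.6% and 41.3%. All four match the stated 63%, 61%, 43% and 41%, so the plan's figures contain no gain from baseline titre.

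**Step 2. Power for a given gain in precision.** Let R² be the share of the variance of the SCR difference that adjustment removes. The SE is multiplied by √(1−R²), and power is that of n/(1−R²) per arm. R² is not in the documents.

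| R² | SE shorter by | B, A strain (64 vs 59) | B, B strain (54 vs 49) | C, A strain (64 vs 60) | C, B strain (54 vs 50) |
|---|---|---|---|---|---|
| 0 | 0% | 63.8% | 61.2% | 43.6% | 41.3% |
| 0.02 | 1.0% | 64.8% | 62.2% | 44.4% | 42.1% |
| 0.05 | 2.5% | 66.3% | 63.7% | 45.8% | 43.3% |
| 0.10 | 5.1% | 68.9% | 66.3% | 48.1% | 45.6% |
| 0.15 | 7.8% | 71.7% | 69.1% | 50.6% | 48.1% |
| 0.20 | 10.6% | 74.5% | 72.0% | 53.4% | 50.7% |

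**Step 3. Where R² might lie.** Trials were simulated with 1275 per arm, Day 29 ln SD 1.5 and a two-fold HAI grid. Assumed values were baseline GMT 20 to 80, baseline ln SD 1.1 to 1.4, and baseline-to-Day 29 correlation 0.3 to 0.7. The estimator was a logistic model with treatment, log baseline titre and an indicator for baseline below 1:10, standardised to a marginal difference with an influence-function SE. With 1000 trials per setting, the simulation error of a single power is up to √(0.25/1000) = 1.6 points.

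- The SE ratio was 0.91 to 0.99, which corresponds to R² = 1 − 0.91² = 0.17 down to 1 − 0.99² = 0.02.
- Power rose by about 2 to 5 points in most settings, 0 to 2 points at correlation 0.7, and 8 to 10 points with low correlation and wide baseline spread.
- Gains were similar for A and B strains.

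A mid-range example (64% vs 59%, baseline GMT 40, ln SD 1.2, correlation 0.5), run with standardisation over four baseline categories, went from 64.2% to 67.2%.

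The slope of log Day 29 titre on log baseline titre explains the pattern. It is correlation × 1.5 / baseline SD. At correlation 0.7 and SD 1.1 it is 0.95, so fold rise is almost unrelated to baseline and little is left to gain. At correlation 0.3 and SD 1.4 it is 0.32, so fold rise falls steeply with baseline.

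**Step 4. Type I error.** In null simulations of logistic standardisation, the one-sided rejection rate was 1.0% to 1.6% adjusted and 0.9% to 1.8% unadjusted, against a nominal 1.25%.

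**Step 5. Consequence for the B strains.** At alpha 0.0125, B-strain GMT power at GMR 1.2 falls from 79.6% to 71.6%. B-strain SCR power falls from 61.2% to 51.1% in Part B and from 41.3% to 31.7% in Part C.

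**Step 6. What 80% would need.** The unadjusted test needs 1800, 1898, 2798 and 2965 per arm in the table's column order. The required R² = 1 − 1275/N is 0.29, 0.33, 0.54 and 0.57.

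**The case against.** Miettinen-Nurminen is customary, prespecified and valid. The stated power assumes the same kind of unadjusted test that the SAP will run, so the plan agrees with itself. The size of any gain rests on a baseline distribution and correlation that neither document gives. All of this stands, and it makes the point one of efficiency.

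Two practical objections also stand. Noninferiority and superiority concern the same SCR difference in the same analysis set. If the methods differ, there are two estimates, and they could disagree near zero. In addition, Protocol 2.9.5.1 itself names Miettinen-Nurminen for comparing SCRs, and 3.9.5.1 and 4.9.5.1 carry it to Parts B and C, so more than one SAP sentence is involved.

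A reader might infer that the SCR analysis throws baseline titre away. It does not, because the titre is part of the seroconversion definition; only its use as a covariate is missing. A reader might also take a gain such as 65% to 72% as typical. That size arises with low correlation and wide baseline spread, and nothing in the documents shows that these strains behave that way.

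**Conclusion.** The SCR superiority tests are valid but less precise than the data allow. Under the assumed ranges in Step 3, adjusting for baseline titre shortens the SE by about 1% to 9%. Power rises by about 2 to 5 points in mid-range settings, with a gain near nil at high correlation and about 8 to 10 points at the favourable extreme, for A and B strains alike. The target difference is unchanged, and the simulations show no clear rise in type I error.

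Two stronger conclusions are not supported. The documents do not show the planned test to be wrong or inconsistent with its stated power. Nor would adjustment cure the low power: R² of 0.54 to 0.57 would be needed for 80% in Part C, against roughly 0.02 to 0.17 here. The change is worth making because it is cheap, but the trial does not depend on it.

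**What to change.** Before Parts B and C are unblinded, amend SAP 3.5.3.4, and Part C through 4.5.3.4 and 4.5.4, as follows.

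- Test SCR superiority with a standardised (g-computation) marginal SCR difference from a logistic model with treatment, log baseline titre and an indicator for baseline below 1:10.
- Use an influence-function or robust CI at the applicable level: 97.5%, or 98.75% when alpha is 0.0125.
- State that the superiority decision rests on the adjusted interval, and report the unadjusted Miettinen-Nurminen interval beside it.
- Keep Miettinen-Nurminen for the coprimary noninferiority tests and add the adjusted difference there as a supplementary row.
- Record the departure from Protocol 2.9.5.1 in SAP Section 5, which now lists no changes. SAP Section 1 lets the SAP prevail where methods differ. If the sponsor regards these tests as key secondary, Protocol 2.9 calls for a protocol amendment.

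The cost is some SAP text, a short program and possibly an amendment, with no new data. The downsides are a less customary interval, two SCR difference estimates for one endpoint, and little gain for strains where baseline titre barely predicts seroconversion.
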